## 6.2 Preparation/Handling/Storage/Accountability

1. The investigator or designee must confirm appropriate temperature conditions have been maintained during transit if applicable, for all study intervention received and any discrepancies are reported and resolved before use of the study intervention.
2. Only participants enrolled in the study may receive study intervention and only authorized site staff may supply or administer study intervention. All study intervention must be kept in a secure environment and stored as per the instructions on the label.
3. The investigator or the head of the institution (where applicable) is responsible for study intervention accountability, reconciliation, and record maintenance (i.e. receipt, reconciliation, and final disposition records).
4. Further guidance and information for the final disposition of unused study interventions are provided in the Investigator Site File.

## 6.3 Measures to Minimize Bias: Randomization and Blinding

Eligible participants will be centrally assigned to randomized study intervention at Visit 1 using an IxRS. The randomization will be stratified by country/region and LVEF (<60%, ≥60%). Additional details will be described in the SAP.

Treatment allocation will be done according to a computer-generated randomization list specified by the sponsor's responsible statistician and provided by the sponsor's randomization management group. Additional details are documented in the IxRS instruction manuals.

Study intervention will be dispensed at the study visits summarized in the SoA. Returned study intervention should not be re-dispensed to the participants.

Tablets containing 10 mg and 20 mg finerenone immediate-release (IR) tablets will differ in size from 40 mg finerenone IR tablets, but will be identical in appearance (size, shape, color) to matching placebo tablets. The packaging and labeling will be designed to maintain the blinding of the investigator's team and the participants. The study data will remain blinded until database lock and authorization of data release according to standard operating procedures.

In compliance with applicable regulations, in the event of a suspected unexpected serious adverse reaction (SUSAR) related to the blinded treatment, the participant's treatment code will usually be unblinded before reporting to the health authorities and ethics committees. For further details, see Section [8.3.6](#).

Bioanalytical staff will be unblinded according to the corresponding Bayer standard operating procedure (SOP). Pharmacometrics staff may also be unblinded according to Bayer SOPs.

Pharmacokinetic and exposure-response analyses will be performed using population approaches (popPK and popPK/PD, e.g. by non-linear mixed effect modeling). Analysis and report will be done under a separate cover. This evaluation might be started prior to database lock. If this is applicable, appropriate measures will be taken to maintain blinding of the study team, e.g. data will be stored separately, and members of the study team will neither have access to the randomization list nor to individual data.

The IxRS will be programmed with blind-breaking instructions. In case of an emergency, the investigator has the responsibility for determining if unblinding of a participant's treatment

assignment is warranted. If the investigator is unavailable, and a treating physician not associated with the study requests emergency unblinding, the emergency unblinding requests are forwarded to the study specific emergency medical advice 24 hours/7 day service. The participant's safety must always be the first consideration in making such a determination. If a participant's treatment assignment is unblinded, the sponsor must be notified within 24 hours after breaking the blind. The date and reason that the blind was broken must be recorded in the source documentation and eCRF, as applicable.

## 6.4 Study Intervention Compliance

To monitor compliance, the investigator will be required to complete a drug dispensing log for each participant. The date of dispensing the study intervention to the participant will be documented.

Overall compliance with study intervention intake should be between 80% and 120% of the scheduled dose at the end of study intervention treatment.

Study intervention will be dispensed according to the schedule provided in the SoA (Section 1.3). Participants will be instructed to bring all unused study intervention and empty packages at every (un)scheduled visit for accountability purposes. Any discrepancies between actual and expected amount of returned study medication must be discussed with the participant at the time of the visit, and any explanation must be documented in the source documents.

## 6.5 Prior and Concomitant Therapy

**General considerations.** Up until recently, there had been no treatment showing unequivocal mortality or morbidity benefit in participants with HFpEF and thus, pharmacologic treatments for HFpEF typically manage symptoms with diuretics being recommended in congested participants in order to alleviate symptoms and signs of HF. Recently, in a study in patients with HFpEF (Anker et al. 2021), SGLT2 inhibition with empagliflozin demonstrated a lower relative risk in the composite of cardiovascular death or hospitalization for heart failure, which was mainly related to a lower risk of hospitalization for heart failure with empagliflozin.

Arterial hypertension is highly prevalent among patients with HFpEF preceding the development of HF and contributing to CV morbidity and mortality by causing substantial CV structural and functional abnormalities by activating the RAAS.

To ensure that a relevant contributor to the development of HF and its outcome is well controlled, participants with uncontrolled blood pressure will be excluded; the treatment of comorbidities in particular arterial hypertension will be at the discretion of the investigator.

All concomitant medication until a participant's last visit will be recorded in the eCRF.

Concomitant therapies **not permitted during treatment with study intervention** are:

- Eplerenone, spironolactone, canrenone, esaxerenone, any renin inhibitor, or potassium-sparing diuretic
- **More than one** of the following: ACEI, ARB, ARNI
- Potent CYP3A4 inhibitors, and potent or moderate CYP3A4 inducers.

**Drug interactions to look out for**

The following should be used with caution, at the discretion of the investigator on a case-by-case basis:

- Potassium supplementation
- Non-steroidal anti-inflammatory drugs (NSAIDs)
- Trimethoprim and trimethoprim / sulfamethoxazole
- Any other medication known to raise potassium levels and/or cause deterioration in renal function.

The investigator is expected to regularly assess the participant's potassium levels and/or renal parameters (e.g. eGFR, creatinine), especially for those receiving these medications. For further details, see the SoA (Section 1.3).

Potassium-lowering agents (e.g. sodium polystyrene sulfonate, calcium polystyrene sulfonate) are allowed to be started during treatment with study intervention following their labeled indication.

Any use of potassium supplementation and potassium-lowering agents must be documented in the eCRF.

A list of the most common CYP3A4 inhibitors and inducers will be provided.

**Caution**

Concomitant use of finerenone in combination with weak or moderate CYP3A4 inhibitors such as: amiodarone, aprepitant, bicalutamide, chloramphenicol, dasatinib, imatinib, lapatinib, mifepristone, nilotinib, norfloxacin, tacrolimus, or verapamil increases finerenone exposure. Additional serum potassium monitoring should be considered, and make finerenone treatment decisions as directed in [Table 6–2](#). More examples of weak or moderate CYP3A4 inhibitors will be provided separately.

**6.5.1      Rescue Medicine**

Not applicable.

## 6.6 Dose Modification

As described in Sections [6.6.1](#) and [4.3](#), the dose of study intervention should be adjusted (up-or down-titration) on the basis of potassium and eGFR levels.

### 6.6.1 Monitoring of Blood Potassium and Dose Adjustment

Guidance for the adjustment of dose after start of study intervention intake based on serum/plasma potassium levels is provided in [Table 6–2](#).

**Table 6–2 Potassium Levels and Guidance for Dose Adjustment**

Serum / plasma potassium (K + mmol/L)	Action to be taken
First sample:	
<5.0	Increase to the next higher dose level (or continue at maximum permitted dose level)
≥5.0 to <5.5	Continue the current dose level
≥5.5 to <6.0	Down-titrate to the next lower dose if possible; if patient is already on dose level 1, interrupt study intervention. K + should be re-checked within 72 h of initial K + result awareness; follow option a
≥6.0	Interrupt study intervention and K + should be re-checked within 72 h of initial K + result awareness; follow option b
Second and subsequent sample:	
Option a <5.5	Continue current dose
≥5.5	Down-titrate to the next lower dose if possible, or interrupt study intervention and recheck K +
Option b <5.5	Restart at dose level 1
≥5.5	Continue to withhold study intervention, further monitoring of K + . Restart at dose level 1 ONLY if K + is <5.0 mmol/L

The following aspects have also to be taken into consideration:

1. If the participant is already on dose level 1 no further decrease is possible after interruption, the same dose level should be re-started once serum/plasma potassium falls below 5.5 mmol/L. Serum/plasma potassium is to be measured at a safety visit 4 weeks ± 7 days after re-starting treatment or dose adjustment.
2. If the participant is on dose level 1 of study intervention, but hyperkalemia recurs soon after a previous event of hyperkalemia leading to interruption of study intervention, and there is no explanation for the recurring hyperkalemia event other than intake of study intervention, premature and permanent discontinuation of study intervention is recommended.
3. In case of hyperkalemia, it is at the investigator's discretion to take measures, including treatment and monitoring in accordance with local practice standards, beyond those reflected in [Table 6–2](#).

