**Please note:**

- 1 month corresponds to 30 days
- Study visits should occur as close as possible to the specified time points in the protocol, but time windows are permitted as specified in the SoA
- At any scheduled or unscheduled visit, the dose of study intervention may be increased to the next possible higher dose, based on serum/plasma potassium level analyzed in the local laboratory and provided the participant was already on a stable dose for 4 weeks ±7 days.

Abbreviations: AE = adverse event; CKD-EPI = Chronic Kidney Disease Epidemiology Collaboration; D = Day; eGFR = estimated glomerular filtration rate; ECG = electrocardiogram; EOS = end-of-study; EQ-5D-5L = EuroQoL Group 5-dimension 5-level questionnaire; hs-TnT = high-sensitivity troponin-t; IxRS = interactive voice / web response system; med. = medication; KCCQ = Kansas City Cardiomyopathy Questionnaire; M = Month; NT-proBNP = n-terminal prohormone B-type natriuretic peptide; NYHA = New York Heart Association; O = on-site; PGIC = Patient Global Impression of Change; PGIS = PGI of Severity; PD = premature discontinuation; PT = post-treatment; SoA = schedule of activities; Tel. = telephone

- Randomization has to occur within 2 weeks of the Screening Visit. If the Screening Visit and Visit 1 (Day 1, Baseline) are performed on the same day, procedures listed for both visits are to be performed only once.
- Study visits to be conducted as a clinic visit or a telephone contact visit. These visits will alternate at 4-monthly intervals from Month 12 onwards with participant contact being made every 2 months.
- This visit should be performed for safety check after any up-titration (4 weeks ±7days) and after restart of study intervention following an interruption for >7 consecutive days. A full unscheduled safety visit should be performed within an adequate timeframe proposed by the investigator after down-titration for reasons other than hyperkalaemia, otherwise only potassium is to be rechecked (refer to [Table 6–1](#))

- d The PD Visit should take place as soon as possible but within 7 days after the last intake of study intervention. If the PD Visit cannot be performed within the timeframe specified, no PD Visit is required. All randomized participants will be followed until the study ends, even if they did not take study intervention or permanently discontinued study intervention.

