### Treatment Period

Following a screening period of up to 2 weeks, eligible participants will be randomized in a 1:1 ratio to either finerenone or placebo. Participants with an eGFR  $\leq 60$  mL/min/1.73 m^2 measured at baseline will start with 10 mg OD (**dose level 1**) with a maximum maintenance dose of 20 mg OD (**dose level 2**), whereas participants with an eGFR  $> 60$  mL/min/1.73 m^2 measured at baseline will start with 20 mg OD (dose level 2) with a maximum maintenance dose of 40 mg OD (**dose level 3**).

There will be at least 2 scheduled visits within the first 3 months from randomization, Visit 2 will take place after 1 month and Visit 3 will take place 3 months after randomization; thereafter, scheduled visits will occur every 3 months until Visit 6 at Month 12. After 1 year from randomization, telephone contact visits will take place at Month 14 and from then onwards every 4 months (i.e. 18 months, 22 months onwards) *alternating* with on-site visits (i.e. 16 months, 20 months, onwards) until the end of the study is reached.

Up-titration is expected to occur after 4 weeks  $\pm$  7 days of treatment at Visit 2 (Month 1). Ideally, each participant will be on the maximum maintenance dose at this point. In the case of elevated potassium values, participants will be down-titrated to the next lower dose. Down-titrations can be performed at any time after the start of study intervention treatment, at any scheduled or unscheduled visit. At any scheduled or unscheduled visit, the dose of study intervention may be increased to the next possible higher dose, based on serum/plasma potassium level and provided the participant was already on a stable dose for 4 weeks  $\pm$  7 days.

Participants will attend an additional unscheduled safety visit 4 weeks  $\pm$  7 days after each up-titration; potassium levels and renal function will be monitored at this safety visit. In addition to the protocol-specified visits, participants may be seen at any time throughout the study at the discretion of the investigator.

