## 4.3 Justification for Dose

Finerenone has been investigated with respect to safety, tolerability, pharmacodynamics and pharmacokinetics (PK) in 29 Phase 1 clinical pharmacology studies. PK were also investigated in all five Phase 2 studies for finerenone (CHF and CKD) with a total of 2017 patients.

The dose regimen of finerenone has been selected based on the results of the completed Phase 2b ARTS-HF and ARTS-DN studies.

The proposed doses for this Phase 3 study are as follows:

- For participants with an eGFR  $\leq$ 60 mL/min/1.73 m^2 at baseline, the starting dose is 10 mg OD. From Visit 2 (Month 1) onwards and if potassium  $<$ 5.0 mmol/l and eGFR decrease is  $<$ 30%, the starting dose can be up-titrated to 20 mg OD  

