**and**
- For participants with an eGFR  $>$ 60 mL/min/1.73 m^2 at baseline, the starting dose is 20 mg OD. From Visit 2 (Month 1) onwards and if potassium is  $<$ 5.0 mmol/l and eGFR decrease is  $<$ 30%, the starting dose can be up-titrated to 40 mg OD.

Note: eGFR according to local laboratory values.

The following rationale for extrapolation to patients with LVEF  $\geq$ 40% of this dose regimen is based on the expected safety profile of finerenone and the applicability of the exposure/response model founded on ARTS-HF data.

In the RALES study, the effect of spironolactone versus placebo on the outcome of patients with HFrEF was investigated and in the TOPCAT trial, HFpEF patients were treated either with spironolactone or placebo. In both studies, changes of serum potassium under spironolactone seem to occur in a similar time-dependent manner in HFpEF and HFrEF patients ([Pfeffer et al. 2015](#)).

In addition, the dose-response relationship is comparable in these two HF populations with potassium increases by 0.37 mmol/L after 3 months of treatment with spironolactone 25 mg in RALES and 0.3 mmol/L after 8 months of treatment with spironolactone in an average dose of 21.7 mg in TOPCAT.

Regarding effects on renal parameters, the dose-response relationship for spironolactone seen in the TOPCAT trial in HFpEF patients and the RALES trial in HFrEF patients was similar indicating that differences in LVEF are not expected to have clinically relevant influence on eGFR changes from baseline (serum creatinine change of 0.16 mg/dL after 8 months for average dose of 21.7 mg in TOPCAT and of 0.10 mg/dL after 3 months for 25 mg spironolactone in RALES).

Overall, the exposure/response relationship for both parameters in HFrEF patients is considered to be applicable for extrapolation to HFpEF patients under the assumption that baseline characteristics with regards to factors influencing PK such as body weight, and

baseline eGFR and baseline potassium levels are similar to that in the ARTS-HF study population. Under these conditions, the expected change of serum potassium is 0.1, 0.2 and 0.2 mmol/L and the expected relative eGFR change from baseline is 2.4, 3.1 and 3.8% for 10, 20 and 40 mg finerenone respectively in the total HF population. These ranges are expected to already represent the worst-case scenario since approximately 79% of the ARTS-HF populations are patients with eGFR  $\leq 60$  mL/min/1.73 m^2.

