**Table 6–1 Dosage of Study Intervention for Administration**

eGFR value at the Baseline Visit, based on local laboratory results:	eGFR 25 to ≤60 mL/min/1.73m 		eGFR >60 mL/min/1.73m 	
Participant randomized to group:	Finerenone	Placebo	Finerenone	Placebo
Starting dose:	10 mg finerenone OD	Placebo OD (Dose Level 1)	20 mg finerenone OD	Placebo OD (Dose Level 2)
Maintenance dose:	20 mg finerenone OD	Placebo OD (Dose Level 2)	40 mg finerenone OD	Placebo OD (Dose Level 3)
Minimum dose after down-titration:	10 mg finerenone OD	Placebo OD	10 mg finerenone OD	Placebo OD
Maximum dose after up-titration:	20 mg finerenone OD	Placebo OD	40 mg finerenone OD	Placebo OD
Study intervention intake	One tablet of study intervention OD, preferably in the morning at approximately the same time each day. Note: Study intervention will be administered at home, except on the day of the first PK visit when the tablet will be taken at the study site			
Missed intake	
 
If discovered within 16 hours after the scheduled time, the participant should take one tablet of study intervention as soon as possible
 
If discovered >16 hours after the scheduled time, this will be considered to be a 'missed' dose and the participant should wait and take the next tablet of study intervention at the usual (scheduled) time.
 
			
Up-titration of dose	
Finerenone
 
 
Up-titrate study intervention to the next possible higher dose based on serum/plasma potassium level
 
eGFR decrease is <30% compared to last scheduled visit.
 
 
Placebo
 
 
Sham-titrate.
 
			
Down-titration of dose	
 
If potassium ≥5.5, down-titrate to the next lower dose level in a step-wise manner (dose level 2 to 1, or dose level 3 to 2)
 
If at dose level 1, interrupt study intervention treatment; study intervention should be re-introduced at dose level 1 as soon as the investigator considers it to be medically justified without compromising safety
 
If in the opinion of the investigator, the participant cannot tolerate the maximum dose level of study intervention, the study intervention dose may be reduced to the next lower dose level.
 
			

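### The K+ <5.0 row of Table 6-2 calls for a dose increase without the eGFR condition set in Section 4.3 and Table 6-1: a limited inconsistency with a small, avoidable safety risk

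*Protocol*

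**What the plan says.** Potassium with an eGFR condition:

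- Protocol Section 4.3 sets two conditions for leaving the starting dose from Visit 2 onwards: potassium below 5.0 ("mmol/l and eGFR decrease is" links the two) and an eGFR decrease below 30%. Only then, for baseline eGFR of 60 or less, "the starting dose can be up-titrated to 20 mg OD". The 20 to 40 mg step for baseline eGFR above 60 has the same two conditions. Section 4.3 does not say what the decrease is measured against.
- Table 6-1, up-titration row, says: "Up-titrate study intervention to the next possible higher dose based on serum/plasma potassium level". It adds an eGFR decrease below 30%, "compared to last scheduled visit". As supplied, the row shows no numerical potassium limit.

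Potassium only:

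- Table 6-2, first sample below 5.0: "Increase to the next higher dose level (or continue at maximum permitted dose level". Neither the other rows nor the three numbered notes mention eGFR.
- The Schedule of Activities note in Section 1.3: "based on serum/plasma potassium level analyzed in the local laboratory and provided the participant was already on a stable dose".
- Section 4.1, Treatment Period: the dose "may be increased to the next possible higher dose, based on serum/plasma potassium level and provided the participant was already on a stable dose".
- Section 8.2.3 (local laboratory) and Appendix 2 (Section 10.2) base titration on local potassium and do not name eGFR.

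Both measures named, without the 30% limit: the synopsis (Section 1.1), the benefit/risk text in Section 2.3, and the opening of Section 6.6, which points to Section 4.3.

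**The concern.** Table 6-2 is a look-up table that turns a potassium result into a dose action. Followed as written, its first row produces an escalation that Section 4.3 and Table 6-1 do not allow whenever potassium is below 5.0 and eGFR has fallen by 30% or more. The protocol's safety argument relies on the double check. Section 2.3 says up-titration follows measured potassium and eGFR, and Section 4.3 supports the 40 mg dose partly because escalation comes only after both are measured. Section 4.3 also associates impaired renal function with higher finerenone concentrations and with more hyperkalaemia and eGFR reduction. What is at stake is an avoidable dose increase in a participant whose renal function has just dropped. No statistical property of the trial is involved.

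**Working it through.** The plan gives no figure to reproduce. The check is whether the dosing texts give the same answer for the same participant.

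**Inputs.** Potassium limit for an increase: 5.0 mmol/L (Table 6-2, Section 4.3). eGFR limit: a decrease below 30% (Section 4.3, Table 6-1). Renal action bands: a fall of 25% to below 40%, and of 40% or more, from baseline (Table 6-3). Starting doses: 10 mg for baseline eGFR of 60 or less, 20 mg above 60. At Visit 2 the last scheduled visit is baseline, so the comparators of Tables 6-1 and 6-3 coincide. The eGFR values below are illustrations, in mL/min/1.73 m².

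**Formulas.** Percentage fall = 100 × (comparator − current) / comparator. The 30% threshold is 0.70 × comparator and the 40% threshold is 0.60 × comparator.

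**Visit 2, potassium 4.5 mmol/L:**

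| | Baseline eGFR 80, on 20 mg | Baseline eGFR 50, on 10 mg |
|---|---|---|
| 30% threshold | 0.70 × 80 = 56 | 0.70 × 50 = 35 |
| 40% threshold | 0.60 × 80 = 48 | 0.60 × 50 = 30 |
| Example value | 50: (80 − 50)/80 = 37.5% fall | 34: (50 − 34)/50 = 32% fall |
| Table 6-2 | increase to 40 mg | increase to 20 mg |
| Section 4.3 and Table 6-1 | do not increase | do not increase |
| Table 6-3 | check and address reversible causes; no dose action | same |

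The instructions conflict at any Visit 2 eGFR of 56 or less (baseline 80) or 35 or less (baseline 50). From above 48 to 56, and from above 30 to 35, Table 6-3 adds no dose action. At a fall of 40% or more it allows down-titration or interruption at the investigator's discretion.

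**Comparator.** After Visit 2 the choice of comparator can change the answer. Take baseline 80, 56 at the previous scheduled visit and 50 now. Against the last scheduled visit the fall is (56 − 50)/56 = 10.7%, which Table 6-1 accepts. Against baseline it is 37.5%, which Section 4.3 would reject if baseline is what it means. Which comparator is clinically better is a separate question; the text needs to use one.

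**The case against.** The strongest defence is that Table 6-2 was never meant to be a complete rule. Its title and the sentence introducing it confine it to potassium guidance. The row also omits the requirement for about four weeks on a stable dose, and nobody would read that silence as a waiver. The opening of Section 6.6, just above the table, bases titration on potassium and eGFR and points to Section 4.3. The synopsis does the same for every visit from Visit 2, and Section 6.1 sends re-escalation to the rules in Table 6-1. Sites obtain local creatinine with potassium, and the eCRF calculates eGFR automatically, so the value is at hand. Investigator judgement applies, and after each up-titration "potassium levels and renal function will be monitored at this safety visit".

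Most of this stands and limits the severity. It does not remove the inconsistency: the row states an action rather than one criterion awaiting another, and the safety visit comes after the dose has been raised.

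A reader might infer three stronger things that the documents do not support:

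- **That Table 6-2 is used on its own.** The caution in Section 6.5 sends sites there when weak or moderate CYP3A4 inhibitors are given. That text is about extra potassium monitoring and does not displace Section 4.3 or Table 6-1.
- **That Table 6-3 was meant to stop the escalation and fails.** It is not an up-titration table. It matters here only because it does not supply the missing condition.
- **That many participants were wrongly escalated.** Section 2.3 reports falls of 30% or more in 5.0% to 12.5% of the finerenone groups in ARTS-HF. It does not say how many of those also had potassium below 5.0, were below the maximum dose and were escalated.

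**Conclusion.** The inconsistency is real but limited. In Amendment 2 the K+ <5.0 row of Table 6-2 omits the eGFR condition required by Section 4.3 and Table 6-1, and four other places repeat the potassium-only basis. Because the synopsis, Section 2.3 and Section 6.6 name both measures, the condition can be recovered from the whole text. What remains is a small, avoidable safety risk from an operational table that gives the wrong action when followed literally. Its frequency cannot be derived from the documents. Alpha, power and the estimand are untouched.

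The conclusion applies to the Amendment 2 wording. SAP Section 1 cites a protocol dated 26 OCT 2022, which was not supplied and may already have corrected the table. SAP Section 3 still carries the potassium-only sentence of Section 4.1, but that does not show what Table 6-2 says in the later version.

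**What to change.** First check the protocol version of 26 OCT 2022. If it has not already done so:

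1. In the K+ <5.0 row of Table 6-2, make the increase conditional on an eGFR decrease below 30% "compared to last scheduled visit", with a pointer to Table 6-1.
2. Name the same comparator in both dose rules of Section 4.3.
3. State the potassium limit of below 5.0 mmol/L in the up-titration row of Table 6-1, if the original table does not carry it.
4. Cross-refer the Schedule of Activities note, Section 4.1, Section 8.2.3 and Appendix 2 to Table 6-1.

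This costs wording in two table rows, one comparator phrase in each of the two Section 4.3 rules, and four cross-references.

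If dosing has ended (SAP version 3.0 is dated 20 JUN 2024), wording changes no longer protect participants. In that case, list from the eCRF the up-titrations made with a local eGFR fall of 30% or more against the last scheduled visit. Local creatinine, the calculated eGFR and dose changes are already recorded there, so the cost is one listing.
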